5.0 STATISTICAL ANALYSIS PLAN

5.1. Analyses.

For all analyses, two-sided tests with significance level $\alpha=0.05$ will be used. Where necessary, assumptions for parametric testing will be checked prior to analyses. If assumption of normal distribution is not met, variable transformation (e.g., log) or nonparametric methods will be used. Randomization scheme should insure comparability of the groups on demographic and medical characteristics. Baseline characteristics will be compared between the groups using ANOVA for numeric values (e.g., age) and chi-square test for categorical variables (e.g., gender). Baseline characteristics found to be different between the groups will be used as covariates in the primary analyses to control for possible effect of group differences on the outcomes. For the primary analysis, PA outcomes will be measured at 2 visits (baseline (BL) and 24 weeks) with the exception of accelerometer and 7DPAR data, which will be measured at 3 visits (BL, 24 weeks, and 48 weeks); cognition and cardiovascular risk factors will also be assessed at 3 visits. Mixed models analyses will be conducted with a) the inclusion of all available data, assuming values missing at random; b) the baseline carry forward (BOCF) imputation method; and c) including only the participants who complete the study. For Hypothesis 1.1, changes in numeric outcomes measuring PA (e.g., time spent on PA, time spent on sedentary behavior) from baseline to week 24 (to week 48 for accelerometer/7DPAR measures) will be compared between the iSTEP and control groups using mixed effects models with subject-specific random effect. Subject-specific random effects will estimate individual changes in outcomes (slopes) as well as individual baseline values (intercept) to take into account natural variability in measured values between subjects. The models will regress PA measures on group (iSTEP vs. control), time (2 time points), and their interaction. A significant interaction term ($p<0.05$) would indicate a significant treatment effect or, in other words, significant differences in mean changes in outcomes over time (slopes) between the two treatment groups. Mixed effects model with terms for group, time (3 visits), and their interaction will be used to evaluate effect of iSTEP intervention on changes in accelerometer values. In explorative analysis, we will compare daily

changes in PA variables measured daily (step count, time spent in PA, and time in SB) between iSTEP and control groups using similar method as above, except using many time points (days) instead of just 2 or 3. For Hypothesis 1.2, Global Mean T-score will measure cognitive performance at all visits; practice effect correction will be applied to values measured at the 24 and 48 weeks. Again, mixed effects model with subject-specific random effect will be used to regress T-score on group (iSTEP vs. control), time (3 time points), and their interaction. We hypothesize that a significant interaction term will show that the slope representing an improvement in cognition will be the smallest for the control group and the largest for the iSTEP group. Similarly, for Hypothesis 2.1, changes in multiple numeric outcomes related to cardiovascular disease risk factors (e.g., cholesterol) will be evaluated with separate mixed effects models. The models will regress the outcomes on group (control, iSTEP PA/SB, iSTEP PA/SB + MedDiet), time (3 time points), and their interaction, including subject specific random effect. We hypothesize that a significant interaction will be observed and that it will show greater improvements in the outcomes for iSTEP groups, with iSTEP PA + MedDiet group having the best results. Similar approach will be used for Hypothesis 2.2, were changes (slopes) in Global Mean T-scores will be compared between the iSTEP PA/SB + MedDiet and iSTEP PA/SB groups and between the iSTEP PA + MedDiet group and controls. Additional analyses: We will conduct exploratory analyses using mixed models to assess changes in diet markers (omega-3, DHA, EPA, percent fat intake on the DHQ) over time to assess if there are group differences and if these markers predict CVD/NP outcome. Multiple regression analyses will be conducted across all participants to examine which factors (PA amount, SB change, MedDiet Score) significantly predict NP and CVD risk factors, including metabolic measures and inflammatory markers at the 6-month and 12-month visits. We will collect Likert scale data that identify what aspect of iSTEP is most useful (e.g., step self-monitoring, step count goals, types of PA/SB messages, comparing PA data to other PLWH) and conduct regression analyses to identify factors (e.g., PA barriers, SMS adherence) that best predict study outcome and PA/diet maintenance.

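### Within H1.1, H2.1 and H2.2, section 5.1 tests several outcomes or contrasts at two-sided 0.05 each, with no lead test and no multiplicity rule

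*Combined protocol and SAP*

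**What the plan says.** All statements below are in section 5.1 (Analyses) of the combined protocol and SAP.

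- **Level and reading.** All analyses use "two-sided tests with significance level" 0.05. In the H1.1 description, an interaction with p<0.05 "would indicate a significant treatment effect".
- **Use of the word primary.** "For the primary analysis, PA outcomes will be measured at 2 visits", "with the exception of accelerometer and 7DPAR data", which are taken at three. The same sentence goes on to cognition and CVD risk factors, so the label spans all three domains.
- **H1.1.** The comparison is of "changes in numeric outcomes measuring PA (e.g., time spent on PA, time spent on sedentary behavior" and similar measures. The list is given by example only.
- **H1.2.** One outcome and one stated contrast: "regress T-score on group (iSTEP vs. control), time (3 time points), and their interaction".
- **H2.1.** "changes in multiple numeric outcomes related to cardiovascular disease risk factors (e.g., cholesterol) will be evaluated with separate mixed effects models", each with three groups. The number of outcomes is not given.
- **H2.2.** Changes in Global Mean T-score are "compared between the iSTEP PA/SB + MedDiet and iSTEP PA/SB groups and between the iSTEP PA + MedDiet group and controls".

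The group comparisons of daily PA data and of diet markers are labelled exploratory. No multiplicity adjustment, ranking of hypotheses or testing order appears.

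**The concern.** If a hypothesis contains several tests, each read at 0.05, and nothing says which one decides it, a favourable p-value on any of them can be presented as support. The error rate for that hypothesis is then above 5%, by an amount that depends on how many outcomes are eventually analysed. For H1.1 and H2.1 that number is open. The power statement in section 5.2 makes no allowance for several tests per hypothesis.

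The trial is meant to examine efficacy and to lay the groundwork for larger mobile interventions. A PA measure or lipid picked out by chance could steer that later work.

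**Working it through.** **The plan's own figure.** Section 5.2 takes 20% dropout from 50 per arm: 50 × (1 − 0.20) = 40, as stated. With 40 per arm and a two-sided 0.05 test, 80% power needs d = (1.960 + 0.842) × √(2/40) = 0.626 SD of the change score. This fits the plan's medium to large effect for two-visit models. The exact d cannot be compared, because the figure is not available. This power is for a single test. The documents state no familywise error rate.

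**Within each hypothesis**, by simulation with no true effects and equal arms of 40 (z tests for contrasts, a chi-square test on 2 df for three-group comparisons):

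| Family | Source of the count | Chance of at least one two-sided p<0.05 |
|---|---|---|
| H2.2, two contrasts | Stated | 9% |
| H1.2 and H2.2, three T-score contrasts | Stated | 11% |
| H1.1, five PA outcomes | Assumed; correlation 0.7 to 0.3 | 15-21% |
| H2.1, four CVD outcomes, three groups | Assumed; correlation 0.7 to 0.3 | 13-18% |

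The H2.2 figure is a little below the independent-test value, 1 − 0.95² = 9.75%, because both contrasts share the combined arm. The 11% takes iSTEP in H1.2 as both intervention arms pooled, as in the abstract. Taking it as one arm of 40, as in the caption to Figure 1a, gives 12%.

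**Across all four hypotheses.** The smallest count the text supports is 2 PA + 1 (H1.2) + 2 CVD + 2 (H2.2) = 7 tests. For independent tests the formula is 1 − 0.95^k: k = 7 gives 30.2%, k = 10 gives 40.1% and k = 13 gives 48.7%. The table below allows for the shared arms, with outcome correlations assumed from 0 up to 0.7 within a domain and 0.3 between domains:

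| PA + CVD outcomes (assumed) | Tests | At least one two-sided false positive |
|---|---|---|
| 2 + 2 | 7 | 25-28% |
| 2 + 3 | 8 | 26-32% |
| 3 + 3 | 9 | 29-36% |
| 4 + 4 | 11 | 32-42% |
| 4 + 6 | 13 | 34-48% |

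**Direction.** These counts include results favouring control. Independent tests at one-sided 0.025 give 1 − 0.975^7 = 16% and 1 − 0.975^13 = 28%, a little over half the two-sided values of 30% and 49%.

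**Why selecting is cheaper than adjusting.** Bonferroni over 7 tests gives 0.05/7 = 0.0071 per test. Power at d = 0.626 falls from 80% to 54%, and the d detectable with 80% power rises to 0.79. A single named test keeps 0.05 and the stated power.

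**The case against.** Four points on the other side have force.

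- **The overall percentage is not a property of the plan.** A reader might infer that the plan carries a fixed false-positive rate of, say, 30-45%. The documents do not support that. PA and CVD outcomes are listed only by example, the minimum count of 7 gives 25-28%, and larger counts go up to 48%. Any such figure is conditional on assumed counts and correlations.
- **Two-sided counts overstate the chance of wrongly declaring benefit.** The plan's hypotheses are directional, and rejections favouring control would not be claimed as efficacy. This roughly halves the figures. They remain inflated against 2.5%.
- **The gap is not everywhere.** A reader might infer that no hypothesis names its outcome, or that every test is confirmatory. H1.2 already has one outcome and one contrast, and H2.2 has one outcome. The daily PA comparisons, including step count, are labelled exploratory, as are the diet-marker models.
- **No passage says that one success anywhere makes the trial positive.** The sentence on interpreting the interaction belongs to the H1.1 models. Whether error should be controlled across four separately stated hypotheses is partly a matter of judgement.

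What remains is the multiplicity within hypotheses. It does not depend on treating the four as one family, and for H2.2 it needs no assumed count. The label of primary analysis does not resolve it, because it covers PA, cognition and CVD factors together.

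**Conclusion.** The point holds for H1.1 and H2.1 (no lead outcome), for H2.2 (no lead contrast), and for the absence of any multiplicity rule. The firmest sizes are those from stated counts: about 9% for the H2.2 pair and about 11% for the three T-score contrasts, against a nominal 5%. The 15-21% for PA and 13-18% for CVD rest on assumed numbers of outcomes and correlations of 0.7 to 0.3. The overall 25-48% rests on 7 to 13 tests, assumed correlations and no true effect on anything. It is illustrative, and the chance of a false result favouring iSTEP is roughly half of it.

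Each mixed model is also to be run under three missing-data approaches, with none named as the lead. If any of the three could support a claim, these figures can only rise.

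**What to change.** In section 5.1, before outcome data are examined:

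- **H1.1:** name one primary outcome and time point, for example accelerometer-measured moderate PA at week 24.
- **H2.1:** name one CVD risk factor as primary, with its time point.
- **H2.2:** name one primary contrast, for example combined intervention versus PA alone on Global Mean T-score.
- **H1.2:** outcome and contrast are already single, so add only the time point.
- **All other non-exploratory outcomes and contrasts:** label them secondary and report estimates with confidence intervals.

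The named outcomes are examples, and the choice is the sponsor's. If error control across the four hypotheses is also wanted, a fixed sequence stated in advance is one option.

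The cost is wording only: no added participants, visits or measurements, and each single primary test is still run at 0.05. The downside is that non-primary outcomes can no longer carry a confirmatory claim. Under a fixed sequence, a missed early test also blocks confirmatory claims on the later ones, and only the first test is certain to keep its stated power.

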
SCHEMA

iSTEP - an mHealth Physical Activity and Diet Intervention for Persons With HIV

DESIGN: Our objective is to assess the efficacy of a mobile phone text message intervention (iSTEP) designed to increase moderate physical activity (PA), reduce sedentary behavior (SB), and improve diet in people living with HIV (PLWH) in order to improve neurocognitive function and reduce cardiovascular disease (CVD) risk. This is a randomized RCT where participants are enrolled into one of three conditions: 1) a Control Group; 2) a PA intervention; 3) a PA + Diet intervention focused on encouraging a Mediterranean-style diet (MedDiet).

POPULATION: PLWH

STRATIFICATION: none

REGIMENT OR INTERVENTION

Assignment to 24-week control group, PA intervention, or PA + Diet Intervention

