5.2 Power Analysis

For all power calculations 20% dropout rate is assumed based on prior mHealth diet interventions¹¹⁹, leaving N=40 for each of the three groups.

For mixed effects models comparing change in outcomes over time between groups, estimates of power depend on intra-class correlation (within-subject correlation of outcomes measured at different times) and number of total visits, including baseline. For models based on 2 visits (hypothesis 1.1, except accelerometer), there will be at least 80% power to detect a medium to large effect size, Cohen's d , for the difference in mean change in outcomes from baseline to week 24 visit (Fig 1a). For models based on 3 visits (accelerometer /7DPAR values in hypothesis 1.1; hypotheses 1.2 through 2.2), there will be at least 80% power to detect a large effect size, d , for mean differences in outcome changes over three visits between any of the two groups (Fig 1b).

[figure not shown]

Figure 1a. Comparing changes in PA outcomes between iSTEP group ($n = 40$ after 20% dropout) and controls ($n = 40$ after 20% dropout) from BL to week 24. **Figure 1b.** Comparing changes in accelerometer data, cardiovascular disease risk factors, or cognitive outcomes between iSTEP PA+MedDiet and either of the other two groups ($n = 40$ for each group after 20% dropout) from BL to 48 weeks.

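### Covariates for the primary models are picked by baseline significance tests after randomisation, none is fixed in advance, and how they enter the group-by-time models is not stated

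*Combined protocol and SAP*

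**What the plan says.** Section 5.1 begins from the premise "Randomization scheme should insure comparability of the groups on demographic and medical characteristics". It then tests that premise: "Baseline characteristics will be compared between the groups using ANOVA for numeric values (e.g., age) and chi-square test for categorical variables". The result feeds the analysis: "Baseline characteristics found to be different between the groups will be used as covariates in the primary analyses", with the declared purpose of guarding against group differences affecting the outcomes. No threshold is attached to the word different, but the section opens by stating for all analyses that "two-sided tests with significance level $\alpha=0.05$ will be used", so selection at p<0.05 is the natural reading.

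No candidate variables are listed and none is always adjusted for. The Schema gives "STRATIFICATION: none", so there are no design factors to carry into the model either.

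The model descriptions in Section 5.1 name no covariate. For Hypothesis 1.1: "The models will regress PA measures on group (iSTEP vs. control), time (2 time points), and their interaction". For Hypothesis 1.2 the plan will "regress T-score on group (iSTEP vs. control), time (3 time points), and their interaction". Hypothesis 2.1 uses the same terms with three groups, and Hypothesis 2.2 a similar approach. All include subject-specific random effects. The treatment effect is the group-by-time interaction. Each model is to be fitted to all available data, with baseline carried forward (BOCF), and in completers.

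**The concern.** There are two separate defects.

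The first is the selection rule. In a properly randomised trial, a significant baseline difference is a chance event by construction. The size of an imbalance says nothing about whether the variable predicts outcome. The rule can therefore adjust for an irrelevant variable and ignore a strong predictor that is moderately unbalanced. The primary model cannot be written down until the data are seen.

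The second is the form of entry. The tested quantity is a difference in change. A baseline covariate entered as a main effect shifts a participant's level equally at every visit, so it cancels from change. Only a covariate allowed to act on change can correct the tested effect. The plan does not say which is meant, so whether the rule meets its own aim depends on a choice left to the analyst.

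At stake is precision in a trial that Section 5.2 describes as powered only for medium-to-large or large effects, and the reproducibility of its primary analysis.

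**Working it through.** **Inputs from the documents.** 150 randomised, 50 per arm (study summary); two-sided alpha 0.05 (Section 5.1); 20% dropout and 40 per arm analysed (Section 5.2). The number of candidate covariates, their correlation with change, and the within-subject correlation are not given in the text (the power figure is not shown). Values used for these are assumptions.

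**1. The plan's own figure.** 50 × (1 − 0.20) = 40 per arm, as stated. With 40 v 40, 80% power corresponds to d = 0.634 on the change scale (t distribution; 0.626 by normal approximation), consistent with the medium-to-large effect claimed for two visits.

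**2. What the baseline test can flag.** The critical value F(2,147) is 3.058. Let g be the largest gap between two arms, in SD units.
- Third arm equal to one of the two: F = (50/3)g², so g = √(3.058/16.67) = 0.428.
- Third arm midway: F = (50/4)g², so g = √(3.058/12.5) = 0.495.

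In 40,000 simulated trials with one variable, 5.0% were flagged. The largest gap was at least 0.3 SD in 29.7%, and it was so without a flag in 24.6%. A run of 400,000 gave 5.0%, 29% and 24%.

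**3. Chance that something enters the model.** For k independent characteristics this is 1 − 0.95^k: 9.8% (k=2), 22.6% (k=5) and 40.1% (k=10).

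**4. Form of entry.** With two visits and complete data, a term βx appears in both y₀ and y₁ and drops out of y₁ − y₀. Mixed models (600 replicates, 50 per arm, true effect 0) were fitted with a 0.5 SD imbalance acting on change, which builds in a bias of 0.15. Mean group-by-time estimates were:

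| Data | No covariate | Main effect | Covariate × time |
|---|---|---|---|
| 2 visits, complete | 0.1465 | 0.1465 | −0.002 |
| 2 visits, 20% lost | 0.146 | 0.145 | −0.007 |
| 3 visits, complete | 0.1533 | 0.1533 | 0.005 |
| 3 visits, 20% lost | 0.151 | 0.150 | −0.003 |

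For two complete visits the standard errors were 0.1888, 0.1888 and 0.1847. With 20% lost, the main effect moved single-trial estimates by 0.014 on average (maximum 0.087) at two visits and by 0.016 (maximum 0.075) at three, but it removed almost none of the bias. These fits used a random intercept. The complete-data identity also holds with a random intercept plus slope and with an unstructured covariance.

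**5. Error rate and power of the rule.** With one covariate acting on change (40 per arm, three arms, 8,000 runs), type I error under the rule was 4.9% at R² = 0.10 and 4.4% at R² = 0.30, so it is not inflated overall. Among the roughly 5% of trials that were flagged, the unadjusted test rejected a true null in 9.1% and 14.3%; adjustment on change brought this to 5.8% and 5.5%. With complete data, main-effect-only entry gives the unadjusted estimate and SE, so it would leave those trials uncorrected.

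Power at d = 0.634 with 10 candidates, 2 of them predictive (6,000 runs per value), where selected covariates do act on change:

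| r with change | Selection rule | Two predictors pre-specified |
|---|---|---|
| 0.1 | 79.1% | 80.1% |
| 0.2 | 79.6% | 82.6% |
| 0.3 | 78.2% | 85.4% |
| 0.4 | 80.1% | 91.6% |

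Unadjusted power was 78.7 to 80.5%.

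**6. Baseline outcome.** Section 5.2 notes that "estimates of power depend on intra-class correlation (within-subject correlation of outcomes measured at different times"). In units of the outcome variance, change has variance 2(1 − ρ) and ANCOVA residual variance 1 − ρ², a ratio of (1 + ρ)/2. For ρ = 0.5, 0.7 and 0.9 the ratio is 0.75, 0.85 and 0.95. Power at d = 0.634 becomes 89.9%, 86.0% and 82.0% (simulated: 89.4%, 85.5%, 81.2%).

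**The case against.** The strongest reply is that little is lost. The rule performs about as well as no adjustment (78 to 80% against 78.7 to 80.5%), and overall type I error is intact. Both statements are right. The harm is a forgone gain and an unpredictable model, not an invalid test.

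The size of the gain also rests on assumed correlations with change. At r = 0.1 there is essentially none, and nothing in the documents shows that age or gender predicts change in any outcome. That stands, and the power figures should be read as illustrations.

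Unflagged gaps of 0.3 SD are not a bias rate, since the unadjusted standard error already allows for chance imbalance. That is also correct. Those figures show only that the rule does not deliver the control it is meant to provide.

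The comparison for Hypotheses 1.1 and 1.2 is ambiguous. The study summary treats iSTEP as both intervention arms, while the caption of Figure 1a has 40 v 40. If the arms are pooled (100 v 50), a two-group test flags at about 0.34 SD, and unadjusted power at d = 0.634 with 80 v 40 is about 90%. The numbers move; the logic does not. No threshold was computed for the chi-square tests.

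Finally, baseline outcome is already in each model as the first visit, and comparing change is a legitimate analysis. It is, but it does not bring the efficiency of ANCOVA. The ANCOVA figures apply to two visits with complete data and do not cover the three-visit outcomes.

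**Conclusion.** The concern holds and should be corrected before analysis. Covariates are selected on chance imbalance, no covariate is fixed in advance, and the form of entry is missing. The missing form of entry is more than a detail. Under an ordinary reading (main effect), the rule leaves the tested effect and its standard error unchanged in the BOCF and completer analyses, and removes almost no imbalance bias in the all-available-data analysis.

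The thresholds of 0.43 to 0.49 SD follow from the plan's sample size and alpha, given a three-arm ANOVA and selection at p<0.05. The power cost depends on assumptions. It runs from about 1 percentage point at r = 0.1, within simulation error, to 11 or 12 points at r = 0.4 for two predictors. Adjusting for baseline outcome by ANCOVA would gain about 2 to 10 points for ρ between 0.9 and 0.5.

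**What to change.** In Section 5.1:

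- Remove baseline significance tests as the covariate rule and present baseline characteristics descriptively.
- Name a short covariate list for each outcome, used whatever the observed balance: the baseline value of the outcome, age and gender for example, and any further variable the sponsor expects to predict that outcome.
- Adjust for the baseline outcome with ANCOVA-type models of the post-baseline visits. Do not use a baseline-by-time term while baseline is also a response row.
- Enter other covariates so that they act on change, as covariate-by-time terms or as covariates in the ANCOVA. State the form, and apply the same set in all three missing-data analyses.

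If the sponsor prefers to keep the change-from-baseline mixed model as primary, the pre-specified list and covariate-by-time entry still resolve the two main defects; only the ANCOVA gain is given up.

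The cost is SAP rewording and a few degrees of freedom, plus a change of primary estimator if ANCOVA is adopted. No new measurements are needed: age and gender are the plan's own baseline examples, and the outcomes are already measured at baseline.

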People who live with HIV (PLWH) experience a high incidence of neurocognitive deficits and HIV-associated non-AIDS (HANA) disorders, including cardiovascular disease (CVD), metabolic dysfunction, and autonomic decline. While antiretroviral treatment (ART) has reduced AIDS-related morbidity, both the virus and the medications are associated with lipid disorders that also increase CVD risk, including dyslipidemia and lipodystrophy. Consequently, the development of effective lifestyle interventions to reduce the incidence of HIV-associated neurocognitive disorders (HAND) and decrease metabolic disorders is a high priority. Physical activity (PA) has been utilized as an effective tool to improve health in PLWH, but may not be sufficient by itself to improve lipid levels. Existing PA interventions in PLWH typically required strenuous PA and significant resources that limit feasibility for many people living with the disease. Recent work indicates that interrupting periods of sedentary behavior (SB), independent of PA, also has a significant beneficial effect on metabolic function, but SB has not been well-studied in PWLH. Mediterranean-style diets (MedDiet) are also effective at improving CVD risk factors in HIV-uninfected individuals and are reported to reduce cognitive decline in persons at risk for Alzheimer's disease, but have not been widely tested in PWLH. We recently developed a novel and personalized Short Message Service (SMS) mobile phone text messaging intervention (iSTEP) that is designed to increase moderate PA in PLWH. Our objective is to expand upon this work and conduct an RCT examining the efficacy of iSTEP in combination with a mobile mHealth MedDiet intervention tailored to PLWH. 150 PLWH will be randomly assigned to a control group ($n = 50$), a 6-month iSTEP group with just a PA/SB intervention ($n = 50$), or a 6-month intervention with both PA/SB and MedDiet components ($n = 50$), where participants receive daily interactive SMS/MMS messages designed to increase moderate PA, reduce SB, and promote adherence to a MedDiet, including walnut consumption. PA/SB will be quantified by accelerometer, Fitbit step counts, and self-report, while MedDiet adherence will be assessed by self-report (Diet History Questionnaire and weekly SMS feedback) and also objective measures (polyunsaturated fatty acid levels - PUFA in blood). We will also conduct a follow-up assessment 6 months after the end of the intervention (accelerometer, neurocognitive testing, PUFA levels) to assess PA and MedDiet adherence. We hypothesize that iSTEP (both intervention arms) will increase PA, reduce SB, and improve neurocognition compared to control; the iSTEP + MedDiet group will demonstrate improvement in CVD risk factors and neurocognition compared to the PA intervention alone. Findings from this proposal will lay the groundwork for development of novel large-scale mobile PA/diet interventions dedicated to treating HAND and improving cardiovascular health for PLWH.

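### Section 5.1 runs the mixed models three ways for missing data and names none as deciding; with unequal dropout, BOCF can move the estimate and the three verdicts can conflict

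*Combined protocol and SAP*

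**What the plan says.** Section 5.1 introduces the primary analysis and then lists three treatments of missing data for the mixed models, side by side:

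- (a) "the inclusion of all available data, assuming values missing at random";
- (b) "the baseline carry forward (BOCF) imputation method";
- (c) "including only the participants who complete the study".

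The general rule is that "two-sided tests with significance level $\alpha=0.05$ will be used". The rule for success is that "A significant interaction term ($p<0.05$) would indicate a significant treatment effect". That sentence does not say in which of the three analyses the interaction must be significant. Nothing in 5.1 or 5.2 calls one analysis primary and the others sensitivity analyses, or says what follows if they disagree.

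Section 5.2 gives the only dropout figure: "For all power calculations 20% dropout rate is assumed based on prior mHealth diet interventions". It is applied equally, leaving 40 per group. No rate by arm is given.

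**The concern.** If (a), (b) and (c) disagree, the plan gives no rule for which result the trial reports. The choice would then be made after the data are seen.

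The three analyses also rest on different assumptions. BOCF gives every person without follow-up a change of exactly zero and carries no uncertainty about that value. It removes any treatment gain in dropouts, and also any change shared by all arms. When arms lose people at different rates, removing a shared change moves the between-arm difference. The completers analysis discards partial data. Neither (b) nor (c) examines departures from MAR in a graded way.

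Unequal dropout is plausible here. Section 4.1 expects some muscle fatigue or soreness from activity, and section 4.2 suspends a participant from the study after an adverse event until written clearance is given again. Both could affect the activity arms more than control.

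**Working it through.** **Inputs from the documents.** 50 randomised per arm (abstract); two-sided alpha 0.05 (5.1); 20% dropout and 40 per group (5.2).

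**Assumptions not in the documents.** Two visits, SD of change 1, correlation 0.5, dropout by arm, and the size of any change common to all arms.

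**1. The plan's own figure.** 50 × (1 − 0.20) = 40, which reproduces. At 40 per arm, 80% power needs d = (1.960 + 0.842) × √(2/40) = 0.626, or 0.634 with the t distribution. This fits the medium-to-large effect that 5.2 describes for two-visit models. The plotted value cannot be checked because the figure is not shown. I use 0.634 as the true effect.

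**2. What BOCF estimates.** Let dT and dC be dropout in the active and control arms, and μT and μC the true mean changes, with dropout at random.

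- Expected difference: (1 − dT)μT − (1 − dC)μC.
- Variance per arm: (1 − d)(1 + μ²) − [(1 − d)μ]².
- Standard error: √((vT + vC)/50).

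Equal dropout of 20%, no common change: 0.8 × 0.634 = 0.507. Variances are 0.864 and 0.800, SE 0.182, ratio 2.78, power 79%. With a common change of 0.5 SD, power is 75%. The MAR group-by-time model gives about 81%. Power falls less than the effect does because the imputed zeros also reduce the variance.

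Dropout 30% active and 10% control, with common change c: the expected difference is 0.7 × (0.634 + c) − 0.9c = 0.444 − 0.2c.

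| c (SD) | BOCF effect | BOCF power | MAR model power | Three analyses disagree |
|---|---|---|---|---|
| 0 | 0.444 | 68% | about 81% | about 16% |
| 0.3 | 0.384 | 53% | about 81% | about 30% |
| 0.6 | 0.324 | 37% | about 81% | about 47% |

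The BOCF columns come from the formulas; simulation agrees to within about 0.01 and one percentage point. The last two columns are simulated. At equal 20% dropout with no common change, the three disagree in about 7% of trials.

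**3. No true effect.** With the same change μ in both arms, BOCF bias is (dC − dT) × μ. At 10% control, 30% active and μ = 0.6, this is −0.20 × 0.6 = −0.12 SD. Variances are 0.776 and 0.932, SE 0.185, ratio −0.65, so type I error is about 10%. If dropout is equal or μ is zero, the bias is zero and type I error is 5%.

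**4. Choosing among the three.** Under the null, the chance that at least one analysis is significant is about 6–7% at equal 20% dropout, and about 12.5% in the unequal case of step 3.

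**5. Completers only.** With no true effect, correlation 0.6, a common change of 0.5 SD, and baseline-dependent dropout of about 30% against 10%, the completers estimate was off by about 0.06 SD and the MAR estimate by 0.002. When the dependence on baseline was the same in both arms, completers bias was only 0.002 SD.

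**The case against.** - **At the planned dropout the damage is small.** With 20% lost in every arm, BOCF costs a few points of power, and picking any of three raises 5% only to 6–7%. This stands. The larger figures depend on dropout differing by arm, and on a common change whose size the documents do not give.
- **A reader might infer that BOCF helps the trial claim a false benefit.** The documents do not support that. The sign depends on which arm loses more people and on the direction of the common change. If all arms improve and the active arm loses more, the false signal runs against the active arm; roughly three quarters of the 12.5% is in that direction. The reverse can also occur: true changes of 1.134 and 0.5 with dropout 10% active and 30% control give 0.9 × 1.134 − 0.7 × 0.5 = 0.67, above the true 0.634.
- **BOCF may be a reasonable assumption.** Return to baseline after leaving a behavioural programme can be defended, and shrinkage is measured against the effect had nobody dropped out. This partly stands, so deleting BOCF is a preference rather than a necessity. But the plan does not argue the assumption, and single imputation still treats the zeros as data.
- **Listing (a) first, and promising all three, gives some protection.** Full reporting would show a disagreement, but it would not resolve one.
- **The arithmetic covers two visits only.** Accelerometer, 7DPAR, cognition and cardiovascular outcomes have three. A person lost after week 24 may keep an observed week-24 change, and the plan does not say how BOCF would treat the visits. For cognition, 5.1 corrects for practice effects, which should reduce the common change; it does not say whether a carried-forward baseline is corrected too.

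**Conclusion.** The concern holds. Section 5.1 leaves the deciding analysis open, and that follows from the text alone. The main consequence is conflicting verdicts with no rule to settle them: about 7% of trials at equal 20% dropout with no common change, and about 16% to 47% under the assumed 10%/30% split as the common change goes from 0 to 0.6 SD.

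BOCF bias is conditional. A false effect needs both unequal dropout and a non-zero common change; at 10%/30% and 0.6 SD it is about 0.12 SD, with type I error about 10%. A reader might also infer that a completers analysis is biased whenever dropout depends on baseline. It is biased when that dependence differs by arm.

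All these sizes rest on the two-visit setting and the assumptions listed with the check. They show what could happen, and do not predict this trial's dropout.

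**What to change.** In section 5.1, before outcome data by arm are seen:

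1. Name (a), the mixed model on all available data from all randomised participants, as the single primary analysis, and tie the interaction rule to it.
2. Label (b) and (c) as sensitivity or descriptive analyses, with no claim resting on them. Say whether completing the study in (c) means having week-24 or week-48 data.
3. Pre-specify a multiple-imputation analysis as the main check on MAR, either control-based or delta-adjusted to a tipping point, preferably in place of BOCF.
4. If BOCF is kept, state how it applies at weeks 24 and 48 and to the practice-corrected T-scores.

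The cost is SAP wording and modest extra programming. The sample size does not change, and no extra participants or data are needed.
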